Cover Page

Study Title: Twitter and Cardiovascular Health

NCT: NCT02806700

PI: [name] MD

University of Pennsylvania

Re: Statistical analysis plan

Last update 10.24.2018

Protocol (Twitter and Cardiovascular Health: Twitter and Hypertension)

Background

Cardiovascular (CV) disease remains the leading cause of morbidity and mortality in the US and is associated with significant economic burden. While there is effective medical treatment for hypertension (HTN) in the form of prescription medications, blood pressure management is likewise dependent on several lifestyle choices. A patient's diet, exercise, monitoring of symptoms and adherence to medication (activities that occur outside of the physician's office), have an effect on clinical outcomes. Social media channels like Twitter offer a new opportunity to explore health related communication generated by the public and for the public about areas such as HTN and its management.

Objectives

This project leverages Twitter, a public online platform, to study if there is a potential benefit of tweeting regularly about health. We will ask patients with a diagnosis of HTN and elevated BP to regularly tweet about health content and evaluate if this intervention will improve their perceived disease management and their systolic blood pressure over a six-month timeframe.

Methods

We will identify patients greater than or equal to 21 years of age, with known HTN (ICD-9 code 401.9) from a single health system. These patients will then be contacted via email. Eligibility questions include: greater than or equal to 21 years of age, not pregnant (self-report), a diagnosis of hypertension and a Twitter account or willingness to create an account for the study.

Eligible patients who consent to participate would then complete a baseline survey and be randomized to the control or intervention group. Randomization will occur via a computerized randomization program in a 1:1 allocation ratio not accessible until after collection of baseline data.

Survey compensation of a gift card worth \$25 would be provided for completion of the final survey at 6 months. Baseline and follow-up surveys will include questions regarding patient activation (PAM-13), self-rated health (SF-1), ideal CV health (BRFSS), HTN self-care practices and demographics. To assess technology use, we will also ask questions from the *Perceived usefulness*, and *Perceived ease of use* surveys. Patients will also consent to having their electronic health records accessed to validate clinical data (e.g. blood pressure (BP), BMI).

Control: The control group study participation would include completing a baseline survey and a survey 6 months later.

Intervention: Participants randomized to the intervention group will be asked to follow the study Twitter account, tweet or retweet health content twice per week using #health and complete a survey at study initiation and 6 months later. Participants will be sent weekly reminders to tweet.

Outcome measures: The primary outcome measure will be change in systolic blood pressure (5mm). The secondary outcome will be patient activation measured by the PAM (a measure of behavior change that has been shown to be changeable over time). Baseline variables will include demographic variables (gender, age, race/ethnicity, and geographic region of residence).

Sample size: Sample size estimates based on the ability to detect a 5mmHg difference in systolic blood pressure at 90% power and type I error of 0.05. We planned to enroll approximately 240 in each control and intervention group, for a total of 480 participants, accounting for a 35% lost to follow up for an online Twitter intervention (total up to 648).

Data analysis: We will use summary statistics to compare demographics and survey responses (health status, ideal CV health status, self-practices perceived usefulness/ease of use) between groups. Categorical variables will be presented as frequencies and percentages and continuous baseline variables will be presented as means and standard deviations (if skewed these will be presented as medians and interquartile ranges).

Our primary outcome will be a 5mmHg change in systolic blood pressure from baseline to study end at 6 months. We will conduct an intent-to-treat analysis. We will use paired t-tests to compare the mean difference in SBP between the intervention and control groups. We will also conduct a multiple linear regression analysis for change in SBP adjusting for covariates which may be imbalanced even after randomization to improve efficiency of our estimates. We will also adjust for baseline SBP. The distribution of change in SBP will be assessed and if it is non-normal (skewed) we will use an appropriate transformation (such as natural log) or we will use a generalized linear model with appropriate family and link choices to model our outcome. For the secondary outcome measure, we will use paired t-test for pre-post differences of PAM scores. A multiple linear regression model will also be used to account for additional imbalances in demographic and baseline health characteristics not evenly distributed by arm. In all models, a binary indicator for control/intervention group will be included. Baseline PAM score will also be adjusted for in the model. Covariates with missing data will be assessed for patterns of missingness and non-ignorability and will be multiply imputed if deemed necessary and reasonable.

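### The 35% loss allowance is added as a multiplier (480 × 1.35 = 648), so 648 keeps 480 evaluable only up to 25.9% loss; if 240 per arm is the evaluable target, power at the stated loss is about 86%, not 90%

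*Protocol*

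**What the plan says.** The sample-size paragraph of the Protocol gives the design basis: "Sample size estimates based on the ability to detect a 5mmHg difference in systolic blood pressure at 90% power and type I error of 0.05". It continues: "We planned to enroll approximately 240 in each control and intervention group", then "for a total of 480 participants, accounting for a 35% lost to follow up for an online Twitter intervention (total up to 648", where the bracket closes.

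The Methods section fixes equal arms: "Randomization will occur via a computerized randomization program in a 1:1 allocation ratio".

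The paragraph gives no standard deviation, does not say whether the 0.05 is one- or two-sided, shows no formula for the loss allowance, and does not say whether 480 counts people enrolled or people with an analysable 6-month systolic blood pressure (SBP). The SAP has no sample-size text, so this paragraph is the only power justification in the two documents.

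**The concern.** A 35% loss removes 35% of whoever is enrolled, so the evaluable target has to be divided by 0.65. The plan's total matches multiplication by 1.35 instead, which gives a smaller number. Enrolling to that ceiling and losing the stated share would leave fewer evaluable participants than the 480 the allowance appears meant to protect.

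What is at stake is the claimed 90% power. A null result would be read against that figure. If the trial's own loss assumption implies less, the result would look somewhat more conclusive than the design supports.

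**Working it through.** **Inputs from the Protocol.** Difference 5 mmHg; power 90%; type I error 0.05; 240 per arm, 480 in total; loss 35%; ceiling 648; allocation 1:1. The SD and sidedness are not given. I take two-sided as the main case and show one-sided beside it. The comparison between arms is treated as a two-sample comparison of means.

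**Reproducing 648.**
- Multiplying: 480 × (1 + 0.35) = 648.0, an exact match.
- Dividing: 480 / (1 − 0.35) = 738.5. With equal arms, 240/0.65 = 369.2, so 370 per arm and 740 in total. This does not match.
- Gap: 740 − 648 = 92.

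**What 648 delivers.**
- Evaluable at 35% loss: 648 × 0.65 = 421.2, or 210.6 per arm.
- Largest loss that still leaves 480: 1 − 480/648 = 0.259, or 25.9%.

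**Power if 240 evaluable per arm gives 90%.** The missing SD cancels, because only the ratio of sample sizes matters. In the large-sample form, two-sided,

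power = Φ[(1.960 + 1.282) × √(n/240) − 1.960].

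At n = 210.6: √(210.6/240) = 0.937; 3.242 × 0.937 − 1.960 = 1.077; Φ(1.077) = 0.859. The noncentral t gives the same 85.9%. One-sided, the noncentral t gives 86.3% (large-sample form 86.4%).

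| Loss, with 648 enrolled | Evaluable per arm | Power (two-sided) |
|---|---|---|
| 25.9% | 240 | 90.0% |
| 30% | 226.8 | 88.3% |
| 35% | 210.6 | 85.9% |

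Difference detectable with 90% power at 35% loss: 5 × √(240/210.6) = 5.34 mmHg.

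The SD that this reading implies is 5 / [3.242 × √(2/240)] = 16.9 mmHg two-sided, or 18.7 one-sided. These are back-solved from the claimed 90% and are not evidence that such an SD was used.

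**Power if 480 enrolled already includes the loss.** Completers are 480 × 0.65 = 312, or 156 per arm. For 90% power at 156 per arm the implied two-sided SD is 5 / [3.242 × √(2/156)] = 13.6 mmHg. Enrolling 648 with 35% loss then gives 210.6 per arm against a target of 156, and power is Φ[3.242 × √(210.6/156) − 1.960] = Φ(1.807), about 96%. There is no shortfall on this reading, but 648 is then a second, unexplained inflation.

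**The case against.** The strongest objection is that the wording speaks of enrolling 240 per arm and describes the 480 as accounting for the loss. Read literally, 480 is an enrolment figure with loss already included, and then there is no power shortfall. This stands as a possibility: without an SD the documents cannot settle it. Against it, 648 is exactly 480 raised by 35%, which has no purpose if 480 already carries the allowance. The evaluable reading is better supported, but the shortfall must stay conditional on it.

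Second, the 86% is measured from a 90% that cannot itself be reproduced. That is true; the firm statement is a drop of about 4 points from a claimed 90% at 240 per arm.

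Third, loss to the online intervention need not mean loss of the primary outcome, since participants consent to health-record access. The Protocol describes that access as a way to validate clinical data, however, and does not say that records will supply 6-month SBP for those lost. The plan itself applies the 35% to a sample size based on SBP. Multiple imputation is planned only for covariates.

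Fourth, the adjusted regression may recover the loss; the data-analysis paragraph speaks of "adjusting for covariates which may be imbalanced even after randomization to improve efficiency of our estimates". Covariates explaining about 12% of the variance (1 − 210.6/240 = 0.1225) would do so in that model. They would not help the t-test, and the sample-size paragraph claims no such gain.

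Finally, 648 is only a ceiling. That does not help: enrolling fewer at the same loss leaves fewer evaluable.

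**Conclusion.** The point holds. As a correction for 35% loss from an evaluable target of 480, 648 is wrong: it covers 25.9% loss and falls 92 short of the 740 needed with equal arms. That part needs no SD.

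The power consequence, about 86% instead of 90%, rests on two assumptions: that 240 per arm is the evaluable target, and that it gives 90% power for 5 mmHg. It also takes the plan's 35% to be loss of the SBP outcome. If 480 was meant as enrolment with loss included, power is not short and the defect is an unexplained 648. On either reading the sentence needs correcting.

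The effect is modest and does not bias the comparison or alter the type I error. It should be fixed because this is the plan's only statement of power.

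**What to change.** Keep 648 and restate the sentence. If 480 is the evaluable target, wording such as this would do:

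> *With 240 evaluable participants per arm (480 in total), the trial has 90% power for a 5 mmHg difference (SD [state], [state one- or two-sided] alpha 0.05). Up to 648 will be enrolled, which keeps 480 evaluable if loss is at most about 26%. At 35% loss about 421 (210 per arm) would be evaluable and power would be about 86%.*

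The SD and sidedness entered should be those actually used; the back-solved values above serve only as a check. If 480 was meant as enrolment with the loss included, say so, give 312 as the evaluable number with its SD, and either explain 648 or delete it.

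The cost is one sentence and, on the evaluable reading, a stated power about 4 points less favourable. Raising enrolment to 740 would also close the gap, but 92 more participants are hard to justify for a loss of that size.

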## Statistical Analysis Plan (Twitter and Cardiovascular Health: Twitter and Hypertension)

We will use summary statistics to compare demographics and survey responses (health status, ideal CV health status, self-practices perceived usefulness/ease of use) between groups. Categorical variables will be presented as frequencies and percentages and continuous baseline variables will be presented as means and standard deviations (if skewed these will be presented as medians and interquartile ranges).

Our primary outcome will be a 5mmHg change in systolic blood pressure from baseline to study end at 6 months. We will conduct an intent-to-treat analysis. We will use paired t-tests to compare the mean difference in SBP between the intervention and control groups. We will also conduct a multiple linear regression analysis for change in SBP adjusting for covariates which may be imbalanced even after randomization to improve efficiency of our estimates. We will also adjust for baseline SBP. The distribution of change in SBP will be assessed and if it is non-normal (skewed) we will use an appropriate transformation (such as natural log) or we will use a generalized linear model with appropriate family and link choices to model our outcome. For the secondary outcome measure, we will use paired t-test for pre-post differences of PAM scores. A multiple linear regression model will also be used to account for additional imbalances in demographic and baseline health characteristics not evenly distributed by arm. In all models, a binary indicator for control/intervention group will be included. Baseline PAM score will also be adjusted for in the model. Covariates with missing data will be assessed for patterns of missingness and non-ignorability and will be multiply imputed if deemed necessary and reasonable.

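### The SBP comparison between arms names a paired t-test that the unmatched design does not support, the PAM t-test is pre-post only, and no analysis is designated primary

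*Protocol*

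**What the plan says.** The analysis text is the same in the Protocol (Methods, Data analysis) and in the SAP.

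- **Allocation** (Protocol, Methods): "Randomization will occur via a computerized randomization program in a 1:1 allocation ratio". No matching or pairing of participants is described.
- **Primary outcome:** "Our primary outcome will be a 5mmHg change in systolic blood pressure from baseline to study end at 6 months".
- **SBP, test named first:** "We will use paired t-tests to compare the mean difference in SBP between the intervention and control groups".
- **SBP, second analysis:** "We will also conduct a multiple linear regression analysis for change in SBP adjusting for covariates which may be imbalanced even after randomization". Baseline SBP is also in this model.
- **Skewness of the change in SBP:** "if it is non-normal (skewed) we will use an appropriate transformation (such as natural log"), or, as the alternative, "we will use a generalized linear model with appropriate family and link choices to model our outcome".
- **PAM:** "For the secondary outcome measure, we will use paired t-test for pre-post differences of PAM scores". A regression adjusted for baseline PAM and for characteristics that differ by arm follows.
- **All regressions:** "In all models, a binary indicator for control/intervention group will be included".

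The Protocol's Outcome measures paragraph lists gender, age, race/ethnicity and region of residence as baseline variables. Only the SBP outcome is called primary. No analysis of it is.

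**The concern.** The test named first for the primary outcome does not match its stated purpose. A paired t-test needs a link between the two measurements in each pair. Here that link exists within a person (baseline and 6 months) but not between a control and an intervention participant.

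The t-test named for PAM has the opposite problem. It is a proper paired test, but of change over time. A change shared by both arms would make it significant with no effect of the intervention.

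The regressions do answer the randomised question, but nothing says that they take precedence. With two unranked SBP analyses, covariates chosen according to observed imbalance, and a model that may be replaced if the data look skewed, the headline SBP result could be settled after the data are seen.

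**Working it through.** **1. Which test fits the SBP sentence.** Let d be a person's 6-month SBP minus baseline SBP. There are three readings.

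- *Pairs formed across arms.* This needs a pairing variable and equal numbers in each arm. The design supplies no pairing variable, and unequal follow-up would break the equality.
- *Each person's change compared between arms.* The estimate is mean(d, intervention) − mean(d, control), with standard error √(s₁²/n₁ + s₀²/n₀). This is a two-sample, unpaired test.
- *A paired test within each arm.* This is a valid paired test, but it does not compare the arms.

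Under none of these do the named test and the stated comparison agree.

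**2. PAM.** The paired statistic is mean(d)/(s/√n). In the intervention arm, mean(d) estimates the change that would have occurred anyway plus the intervention effect, and the test cannot separate the two. The planned model, 6-month PAM = a + b·arm + c·baseline PAM, estimates the randomised contrast as b.

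**3. Does the sample size show which SBP test was meant?** The Protocol (Sample size) gives 5 mmHg, 90% power, type I error 0.05 and 240 per arm, but no SD. The figure therefore cannot be reproduced, only solved backwards (two-sided, z-values 1.960 + 1.282 = 3.2415 before rounding):

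- two-sample test: SD = 5 × √(240/2) / 3.2415 = 54.77/3.2415 = 16.9 mmHg;
- 240 pairs: SD = 5 × √240 / 3.2415 = 77.46/3.2415 = 23.9 mmHg.

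With no SD stated, the sample size does not settle the reading.

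**4. Effect of having no designated primary analysis.** Take only two candidates: the unpaired test on change, and the regression on arm and baseline SBP. Assume equal SDs at both visits and baseline–follow-up correlation r (not stated in the documents). In SD units the two estimates are Δy − Δx and Δy − rΔx, where Δy and Δx are the between-arm differences at 6 months and at baseline. Their variances are proportional to 2(1 − r) and 1 − r², and their covariance to 1 − r². The correlation between the two test statistics is therefore √((1 + r)/2).

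The chance under the null that at least one exceeds ±1.96 follows from the bivariate normal distribution:

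| r | correlation of tests | either significant | simulated, 240 per arm |
|---|---|---|---|
| 0.3 | 0.806 | 7.8% | 7.9% |
| 0.5 | 0.866 | 7.3% | 7.2% |
| 0.7 | 0.922 | 6.8% | 6.9% |

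The simulation used 60,000 null trials per row. Each test alone rejected in about 5% of them. Choice of covariates or of transformation is not included.

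**5. The log example.** The natural log does not exist at or below zero, and a change in SBP takes both signs. If change is coded as a fall and is normal with mean m and standard deviation SD, the share without a logarithm is Φ(−m/SD):

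| SD (assumed) | m = 0 | m = 5 mmHg |
|---|---|---|
| 12 | 50% | Φ(−0.417) = 34% |
| 16.9 | 50% | Φ(−0.296) = 38% |
| 20 | 50% | Φ(−0.25) = 40% |

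Coded as 6 months minus baseline, the share at SD 16.9 is 50% to 62%. Dropping these participants would conflict with the intent-to-treat statement in the same paragraph.

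**The case against.** The strongest reply is that the SBP sentence is only loosely worded. The outcome is a change from baseline and the PAM sentence uses pairing for pre-post differences, so pairing probably means forming each person's change before the arms are compared. That is the most natural reading, and it makes this a naming error and not a demonstrated bias. It still leaves the wrong test in both documents.

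Several stronger readings are tempting and are not supported:

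- *No valid between-arm analysis is planned.* Not so: both outcomes have a regression with an arm indicator and the baseline value.
- *The paired test would inflate error.* In simulation, arbitrary pairing of equal arms kept the error between 4.7% and 5.3%. With unequal arms the test would simply not run.
- *A significant pre-post PAM test would be reported as efficacy.* The plan never says so. As a test of change over time, it is correct.
- *Covariates are entirely unspecified.* The Protocol lists demographic variables, and baseline SBP and baseline PAM are fixed. What is missing is the rule for choosing among the rest, and which health characteristics count.
- *The false-positive rate of the plan is 7% to 8%.* That holds only if the more favourable p-value is chosen. The order of the text could also be read as unadjusted main and adjusted supportive, but that ranking is not stated, and it would put the misnamed test first.
- *The log is required.* It is an example, and an analyst could judge it inappropriate. The gap is the absence of any criterion, family or link.

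**Conclusion.** The point holds as one of wrong test naming and incomplete pre-specification. The paired t-test is wrong for the SBP comparison between arms, the PAM t-test does not estimate the randomised effect, no analysis is designated primary, and the skewness clause offers an example that a signed change score cannot take. These follow from the text and need no assumption.

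The sizes are illustrative. Choosing the better of two SBP analyses would give about 7% to 8% false positives instead of 5%, under assumed correlations of 0.3 to 0.7 and equal SDs at the two visits. A log of the fall would be undefined for roughly 34% to 50% of participants, under normal change, SD 12 to 20 mmHg and mean fall 0 to 5 mmHg. The harm is moderate because sound between-arm models are already in the plan. It should be fixed, but it does not undermine the design. Whether 5 mmHg belongs in the outcome definition is a separate, minor matter.

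**What to change.** Change the same text in the Protocol and the SAP:

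1. Designate one primary analysis: linear regression of 6-month SBP (or change in SBP) on arm and baseline SBP, in mmHg, reporting the arm coefficient with its 95% confidence interval. Fix any further covariates in advance or keep them to a sensitivity analysis.
2. Replace the paired t-tests for SBP with an unpaired (Welch) two-sample t-test on change, labelled supportive.
3. Make the regression on arm and baseline PAM the main PAM analysis, with within-arm pre-post results descriptive only.
4. Delete the log of the change score. Keep the primary model on the mmHg scale whatever the distribution, and fix the standard-error method in advance, for example robust standard errors always. Any GLM or transformation is a sensitivity analysis with its form stated.

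A different valid between-arm analysis could be made primary, provided that one is named. The baseline-adjusted regression is preferred because it is already planned and loses no power. With SD of change 16.86 mmHg (the value giving 90% power by the exact t-test) and 240 per arm, simulated power for 5 mmHg was 98%, 96% and 94% at correlation 0.3, 0.5 and 0.7, against about 90% for the Welch test. Staying on the mmHg scale is safe at this size. With residual skewness of 2, ordinary standard errors rejected in 5.1% and 5.0% of null trials, and robust (HC3) ones in 5.0% and 4.9%, at 240 and 156 per arm (156 = 240 × 0.65).

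The cost is wording only: no added data or participants.
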